2.1.4.2 Adverse events variables

All reported AEs and SAEs is collected from the time of signed informed consent until the end of the study (defined as patient's last visit planned per protocol or the resolution/stabilization of all SAE and AEs with pre-specified monitoring). All events will be managed and reported in compliance with all applicable regulations, and included in the final clinical study report.

All AEs and SAEs will be coded to a "LLT", "PT", "HLT", "HLGT" and associated primary "SOC" using MedDRA. MedDRA terms for hypersensitivity and injection site reactions will be included. The occurrence of AEs and SAEs is recorded from the time of signed informed consent until the end of the study.

If an AE/SAE is ongoing and not resolved by the end of the study observation period and leads to subsequent death of the patient, it will have to be reported.

The AE observations will be classified per the observation periods of safety data as defined above into:

- **Pre-treatment AEs** are AEs that developed or worsened or became serious during the pre-treatment period.
- **Treatment-emergent AEs (TEAE)** are AEs that developed or worsened or became serious during the 12-month on-treatment period.
 - The **6-month TEAEs** are AEs that developed or worsened or became serious during the 6 month on-treatment period.
to be used at time of 6-month database lock only.
- **Post-treatment AEs** are AEs that developed or worsened or became serious during the post-treatment period.

Symptomatic overdose

Symptomatic overdose with IMP/anti-hyperglycemic non-investigational medicinal product (NIMP) will be identified through a specific question on the AE page in the e-CRF.

Pregnancy

Pregnancy occurring, either in female subject or in a female partner of a male subject, entered in a study will be identified through a dedicated AE page in the e-CRF.

2.1.4.3 Injection site reactions, hypersensitivity reactions and immunogenicity

No immunogenicity assessment is planned as part of the protocol (1).

Injection site and hypersensitivity reactions are AEs recorded on AE page and identified for the statistical analysis using the following MedDRA codes:

- Injection site reactions will be identified using the following MedDRA searches: HLGT "Administration site reactions" and HLTs "Administration site reactions NEC", "Infusion site reactions", "Injection site reactions" and "Application and instillation site reactions" and excluding HLTs "Implant and catheter site reactions" and "Vaccination site reactions".

- Hypersensitivity reactions will be identified using the following MedDRA searches: Angioedema standardized MedDRA query (SMQ) (Narrow), Severe cutaneous adverse reactions SMQ (Broad), Hypersensitivity SMQ (Broad and Narrow) and excluding PTs related to administration, application, injection and infusion sites. High level term “Anaphylactic Responses” are included in those SMQs.

2.1.4.4 Deaths

The death observations are per the observation periods defined above. In addition, after the post-treatment period, death related to IMP as well as death resulting from TEAE must be reported to the Sponsor.

- Death on-study: deaths occurring during the on-study observation period (defined as the time from the signed informed consent date up to the end of the study, ie, last protocol planned visit or the resolution/stabilization of all SAE),
- Death pre-treatment: deaths occurring before the on-study observation period,
- Death on-treatment: deaths occurring during the on-treatment period,
- Death post study: death occurring after the end of study.

2.1.4.5 Laboratory safety variables

The clinical laboratory data consist of blood analysis (including, LFTs namely AST, ALT, ALP, total bilirubin, ALP, and creatinine) at Screening. They are not considered as part of safety endpoints to evaluate the study objectives during the treatment period.

2.1.4.6 Vital signs variables

Vital signs include: observed and change from baseline of heart rate (bpm), systolic and diastolic blood pressures (mmHg), and weight (kg) at baseline, 6 months and 12 months.

2.1.4.7 Electrocardiogram variables

Electrocardiogram (ECG) is not done routinely in the protocol (1). It may be done at the discretion of the investigator when clinically indicated. This data is not routinely recorded in the e-CRF and if abnormal, should be recorded as an AE.

2.1.5 Pharmacokinetic variables

Not applicable.

2.1.6 Pharmacodynamic/genomics endpoints

Not applicable.

2.1.7 Quality-of-life endpoints and patient reported outcomes

Patients will complete self-reported questionnaires at designated time points in the study.

2.1.7.1 Diabetes Treatment Satisfaction Questionnaire Status Version

The DTSQs is a validated questionnaire to assess patient satisfaction with treatment and patient perception of BG control (3). The DTSQs will be used to evaluate patient satisfaction with treatment and patient perception of BG control over a several week period. The DTSQs is comprised of 8 questions which are answered on a Likert scale from 0 to 6. Responses to these questions would be summarized into the three domain scores of Total Treatment Satisfaction (Questions 1, 4-8), Hyperglycemia Perception (Question 2) and Hypoglycemia Perception (Questions 3) such that a higher score would be indicative of better satisfaction. Mean differences in scores between groups would be evaluated to understand the impact of treatment on patient satisfaction. DTSQs will be evaluated at Screening, Day 1, 6 months and 12 months in this study.

The total treatment satisfaction score and the 2 other scores are determined by computing the mean of item responses:

- Total treatment satisfaction score: sum of Items 1, 4, 5, 6, 7 and 8, ranging from 0 (no satisfaction) to 36 (high satisfaction),
- Perceived frequency of hyperglycemia score: Item 2, ranging from 0 (none of the time) to 6 (most of time),
- Perceived frequency of hypoglycemia score: Item 3, ranging from 0 (none of the time) to 6 (most of time).

The DTSQs endpoints are:

- Average scores on total treatment satisfaction from DTSQs at 6 months and 12 months,
- Average scores on hyperglycemia perception from DTSQs at 6 months and 12 months; and,
- Average scores on hypoglycemia perception from DTSQs at 6 months and 12 months.

Additionally, on these 3 scores (total treatment satisfaction, hyperglycemia perception and hypoglycemia perception), evaluation will be performed on:

- Change from baseline to 6 months,
- Change from baseline to 12 months,
- Change between 6 and 12 months.

Additional endpoints are:

- Percentage of patient responders on total treatment satisfaction score, defined as patients presenting a change from baseline to respectively Month 6 and Month 12 of at least the distribution-based minimal clinically important difference (MCID) value ([Section 2.5.1](#)).
- Percentage of patient responders on perceived frequency of hyperglycemia score, defined as patients presenting a change from baseline to respectively Month 6 and Month 12 of at least the standard MCID value ([Section 2.5.1](#)).

- Percentage of patient responders on perceived frequency of hypoglycemia score, presenting a change from baseline to respectively Month 6 and Month 12 of at least the standard MCID ([Section 2.5.1](#)).

2.1.7.2 Diabetes Treatment Satisfaction Questionnaire Change Version

The DTSQc was developed from the original DTSQ to evaluate the change in treatment satisfaction at a specific time point (4).

The DTSQc will be used to produce a measure of relative change in satisfaction rather than measure of absolute satisfaction, which is subject to ceiling and floor effects.

A score for DTSQc treatment satisfaction items (Questions 1, 4-8) range from -3 to +3, and the sum of the treatment satisfaction scores range from -18 to +18.

Positive scores are indicative of increases in treatment satisfaction relative to one year ago (start of the study).

Perceived hyperglycemia (Question 2) and hypoglycemia (Question 3) items have scores that range from -3 to +3 in the DTSQc, with higher scores indicating more frequent perceived hyperglycemia or hypoglycemia by the end of the study.

To control for baseline scores, DTSQs will be used as a measure of treatment satisfaction at baseline. DTSQc will be evaluated at 12 months in this study.

The total treatment satisfaction score and the 2 other scores are determined by computing the mean of item responses:

- Total treatment satisfaction score: sum of Items 1, 4, 5, 6, 7 and 8, ranging from -18 (deterioration in treatment satisfaction) to +18 (improvement in treatment satisfaction),
- Perceived frequency of hyperglycemia score: Item 2, ranging from -3 (fewer problems than before with hyperglycemia) to +3 (more problems),
- Perceived frequency of hypoglycemia score : Item 3, ranging from -3 (fewer problems than before with hypoglycemia) to +3 (more problems).

The DTSQc endpoints are:

- Average scores on change in total treatment satisfaction from DTSQc at 12 months,
- Average scores on change in hyperglycemia perception from DTSQc at 12 months,
- Average scores on change in hypoglycemia perception from DTSQc at 12 months.

2.1.7.3 Hypoglycemia Patient Questionnaire

Patients will also complete the Hypoglycemia Patient Questionnaire, detailed in Appendix H of Achieve Control protocol (1).

This questionnaire will require them to report frequency of hypoglycemia experienced during the course of the study. Responses to Questions 4 and 5 on the Hypoglycemia Patient Questionnaire will be used to assess the endpoints. A patient report of one or more episodes of either moderate or severe hypoglycemia since the last visit will be indicative of patient experience of hypoglycemia.

The Hypoglycemia Patient Questionnaire endpoints are:

- Proportion of patients who report moderate or severe hypoglycemia since last visit on the Hypoglycemia Patient Questionnaire (Questions 4 and 5) at baseline, at 6 months and at 12 months.

2.1.7.4 Global Effectiveness Scale

Patient and Physician reported GES: This measure, originally developed to assess the impact of treatment on asthma control, will be adapted for diabetes (GES). The GES assesses impact of treatment on a 5-point scale:

- Complete control of diabetes,
- Marked improvement of diabetes,
- Discernible, but limited improvement in diabetes,
- No appreciable change in diabetes,
- Worsening of diabetes.

These assessments will be completed twice by patients at 6 and 12 months. Physicians will complete the GES twice for each patient they manage at 6 and 12 months.

The GES endpoints are:

- Proportions of patient and provider reported “Complete control of diabetes” or “Marked improvement of diabetes” responses to GES question at 6 months and 12 months.

2.1.8 Health economic endpoints

The healthcare utilization endpoints are:

- Mean number and proportion of patients with hospitalizations over a 6 month and 12 month period,
- Mean number and proportion of patients with emergency room visits over a 6 month and 12 month period,
- Mean number of provider office visits and proportion of patients with specialty visits over a 6 month and 12 month period,
- Mean overall and diabetes-related costs at 6 months and 12 months.

2.2 DISPOSITION OF PATIENTS

Screened patients are defined as any patient who met the inclusion criteria and signed the informed consent.

All randomized patients will be included in the Intent-to-Treat (ITT) Population.

Patients will not be randomized more than once.

For patient study status, the total number of patients in each of the following categories will be presented in the clinical study report using a flowchart diagram or summary table:

- Screened: all patients who originally met inclusion criteria and signed the informed consent³,
- Screen failure patients and reason for screen failure³,
- Non-randomized but treated patients³,
- Randomized: all screened patients with a treatment arm allocated and recorded in the IRT database, regardless of whether IMP was used or not and regardless of use of a PSP program³,
- Randomized but not treated patients³,
- Randomized and treated patients³,
- The **12-month treatment completer population** (presented as randomized): patients who complete the 12-month treatment period (have performed Visit 4 [D360]) without permanently discontinuing treatment²,
- The **6-month-treatment completer population** (presented as randomized): patients who complete the 6-month treatment period (have performed Visit 3 [D180]) without permanently discontinuing treatment¹,
- Patients who permanently discontinued treatment during the 12-month study period and reason for permanent treatment discontinuation presented as randomized²,
- Patients who permanently discontinued treatment during the 6-month treatment period (before Month 6) and reason for permanent treatment discontinuation presented as randomized¹,
- Patients who permanently discontinued treatment at or after the 6-month treatment period and reason for permanent treatment discontinuation presented as randomized²,

1. Used at time of 6 month database lock,

2. Used at time of 12 month database lock,

3. Used for 6 month and 12 month database lock.

For all categories of patients (except for the screened and non-randomized categories) percentages will be calculated using the number of randomized patients as the denominator. Reasons for treatment discontinuation will be supplied in tables giving numbers and percentages by treatment group. This summary will be provided by treatment group within each center and will also be further sub-grouped by geographic region.

Kaplan-Meier (KM) plots and estimates of the cumulative incidence of IMP discontinuation based on CRF collected data will be performed.

All critical or major deviations potentially impacting efficacy analyses, randomization, and drug-dispensing irregularities, and other major or critical deviations will be summarized in tables giving numbers and percentages of deviations by treatment group.

Additionally, the analysis populations for safety and efficacy will be summarized in a table by number of patients on the randomized population ([Section 2.3](#)).

2.2.1 Randomization and drug dispensing irregularities

On V2 (Day 1), the investigator or designee contacts the IVRS/IWRS and provides the patient number provided by IVRS/IWRS at screening visit, date of birth, HbA1c, individualized HbA1c target (<8%/<7%), GLP-1 RA use (y/n), SU use (y/n) and HbA1c (<9%/≥9%). Afterwards the IVRS/IWRS is called again each time for each new visit but does not include “standard of care” visits, which are not considered trial visits.

Treatment kits are not dispensed since the drugs are provided through a pharmacy. The investigator provides the patient with a prescription for the insulin and a card to provide to the pharmacy to obtain the insulin, a “smart card” as a method of reimbursement.

Randomization will be performed centrally by IVRS/IWRS, and will be stratified by individualized HbA1c target (<8%/<7%), GLP-1 RA use (y/n), SU use (y/n) and HbA1c (<9%/≥9%). a patient cannot be randomized more than once in the study. Patients who need to be moved to another site will have a new randomization number assigned at the new site.

Randomization and drug-dispensing irregularities occur whenever:

1. A randomization is not in accordance with the protocol-defined randomization method, such as,
 - a) An ineligible patient is randomized,
 - b) A patient is randomized based on an incorrect stratum,
 - c) A patient is randomized twice.OR,
2. A patient is dispensed/prescribed an IMP not allocated by the protocol-defined randomization, such as,
 - a) A patient at any time in the study is dispensed/prescribed different IMP than as randomized (which may or may not contain the correct-as-randomized IMP), or,
 - b) A non-randomized patient is treated with IMP reserved for randomized patients.

Randomization and drug-dispensing irregularities will be monitored throughout the study and reviewed on an ongoing basis.

All randomization and drug-dispensing/prescription irregularities will be documented in the clinical study report. If the number of irregularities is large enough to make a tabular summary useful, the irregularities will be categorized and summarized among randomized patients (number and percentages). Non-randomized, treated patients will be described separately.

Patients with the following deviations will be identified and described in separate listings:

- Treated but not randomized,
- Randomized but not treated,
- Randomized but not following the treatment arm as randomized.

Randomization and drug-dispensing irregularities to be prospectively identified include but are not limited to:

Table 3 - Randomization and drug allocation irregularities

Randomization and drug allocation irregularities
Treatment dispensation without IRT transaction
Erroneous treatment delivery
Treatment not available
Randomization by error
Patient randomized twice
Forced randomization
Stratification error
Patient switched to another site

2.3 ANALYSIS POPULATIONS

Patients treated without being randomized will not be considered randomized and will not be included in any safety or efficacy population.

Patients who are dispensed/prescribed study drug without calling the IRT or before calling the IRT are considered non-randomized patients. They are excluded from any population for analysis, including efficacy and safety. However, if these patients experienced any significant safety event, they should be documented separately in the clinical study report.

The randomized population includes any patient who has signed her/his informed consent and has been allocated to a randomized treatment arm regardless of whether the treatment was delivered or used.

The safety and efficacy populations will be defined at time of 6-month data base-lock based on data collected during the 6 month-randomized period.

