2.3.1 Efficacy populations

The efficacy population is the ITT population, defined as all randomized population, irrespective of the treatment actually received, analyzed according to the treatment group allocated by randomization.

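### SAP 2.3 removes patients prescribed study drug before the IRT call from every population, with no exception for those then allocated an arm, which conflicts with the ITT definitions

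*SAP*

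**What the plan says.** SAP 2.3 contains this rule: "Patients who are dispensed/prescribed study drug without calling the IRT or before calling the IRT are considered non-randomized patients". The consequence follows at once: "They are excluded from any population for analysis, including efficacy and safety". Significant safety events in these patients are to be documented separately in the study report.

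Other text defines randomization by allocation alone:

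- SAP 2.3, after the exclusion, puts in the randomized population any consenting patient who "has been allocated to a randomized treatment arm regardless of whether the treatment was delivered or used".
- SAP 2.2 counts as randomized "all screened patients with a treatment arm allocated and recorded in the IRT database, regardless of whether IMP was used or not", and adds: "All randomized patients will be included in the Intent-to-Treat (ITT) Population".
- SAP 2.3.1 defines the efficacy population as "all randomized population, irrespective of the treatment actually received, analyzed according to the treatment group allocated by randomization".
- Protocol 11.2 and 11.3.1.1 likewise place all randomized patients in ITT by allocated arm.

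Protocol 11.3.2 excludes non-randomized but treated patients from the safety population. It has no rule that reclassifies a patient to whom an arm was allocated. SAP 1.5, which lists changes to the protocol's statistical section, does not mention this exclusion.

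**The concern.** The exclusion names two situations: no IRT call, and study drug prescribed or dispensed ahead of the call. A patient in the second situation can go on to be allocated an arm. That patient meets every definition of randomized in both documents, yet SAP 2.3 calls the patient non-randomized. A programmer building the population flags cannot satisfy both rules.

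At stake is whether the primary analysis is the ITT analysis it claims to be, and whether an allocated and treated patient is counted in the safety population. The situation can arise in practice. In the US (about 439 sites) study insulin is obtained at a pharmacy on an ordinary prescription. In Canada (20 sites) the site dispenses it. In neither country does the IRT control dispensing (protocol 8.4 and 8.7).

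**Working it through.** **1. The definitions applied to one patient.** Take a consenting patient prescribed insulin in the morning and allocated an arm by the IRT in the afternoon. I read the call in SAP 2.3 as the Visit 2 randomization call; the system is also contacted at Visit 1 for a patient number.

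| Text | Status of this patient |
|---|---|
| SAP 2.3, exclusion rule | Non-randomized; in no population |
| SAP 2.3, randomized population | Randomized |
| SAP 2.2 | Randomized; in ITT |
| SAP 2.3.1 | In the efficacy population, allocated arm |
| Protocol 11.2, 11.3.1.1 | In ITT, allocated arm |

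A patient for whom the IRT was never called has no allocation, so excluding that patient conflicts with nothing. The opening sentence of SAP 2.3 already covers patients treated without being randomized.

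**2. How comparable errors are treated.** SAP 2.2.1 handles randomization of an ineligible patient, a wrong stratum, and prescription of an insulin other than the one allocated as irregularities to document, with no stated removal from ITT. SAP 2.3.2 keeps a patient randomized twice under the first allocation.

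**3. The plan's own figures.** Inputs from SAP 1.3: response 33% against 38.5%, two-sided alpha 0.05, power 90%, 1:1 allocation.

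- n = [1.960·√(2·0.3575·0.6425) + 1.282·√(0.33·0.67 + 0.385·0.615)]² / 0.055² = 1594 per arm. With continuity correction it is 1630. The SAP states 1635, within 3% of either.
- Interim at t = 1800/3324 = 0.5415. Alpha spent = 0.05·(e^(3t) − 1)/(e³ − 1) = 0.0107. Interim power is 45.3%, against 45% stated.
- Overall power at 1662 per arm is 90.8%, from two correlated normal statistics with correlation √(900/1662) and final mean 0.055·√1662/√(0.33·0.67 + 0.385·0.615) = 3.31. The boundaries are the recomputed nominal levels, 0.0107 and 0.0453.

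**4. Cost in numbers if the rule is applied evenly.** The frequency is not in the documents; the range is assumed. The interim is held at 900 per arm.

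| Excluded | Patients of 3324 | Overall power |
|---|---|---|
| 0% | 0 | 90.8% |
| 0.5% | 17 | 90.6% |
| 1% | 33 | 90.5% |
| 2% | 66 | 90.2% |
| 5% | 166 | 89.3% |

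**5. Shift if only the Toujeo arm loses patients.** Removing a share e who respond at rate r changes the rate by (0.385 − e·r)/(1 − e) − 0.385.

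| e | r = 33% | r = 0 (bound) |
|---|---|---|
| 1% | +0.06 points | +0.39 points |
| 3% | +0.17 points | +1.19 points |

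The 33% column uses the planning rate for the comparator. The last column assumes that every removed patient fails.

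**The case against.** The strongest reply has three parts.

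**The text does not say that allocated patients are dropped.** That is so: SAP 2.3 does not spell out what happens when a call follows. The rule could be read, together with the definitions around it, as covering only patients handled outside the IRT. But it lists prescription ahead of the call as its own case and gives no exception, so the narrow reading has to be supplied by the reader. This part reduces the point to an unresolved conflict between rules. It does not remove it.

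**The trigger precedes allocation.** Randomization is central, so an exclusion based on something that happened before allocation is independent of arm if applied evenly. This stands.

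**Detection need not depend on arm.** A reader might infer that an early comparator prescription goes unnoticed when the patient draws the comparator and shows up when the patient draws Toujeo, so that the rule favours one arm. The documents do not support that as a finding. The US smart-card vendor's fill dates and the Canadian tracking log (protocol 8.8) are kept without regard to arm. A prescription that does not match the allocation is already an irregularity under SAP 2.2.1. Arm-dependent identification remains possible in an open-label trial, because no document says how early prescriptions are to be found.

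On safety, separate documentation of significant events in SAP 2.3 and separate listings in SAP 2.3.2 soften the loss. They do not put an allocated, treated patient back in the safety population.

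**Conclusion.** The conflict is real: one stated rule in SAP 2.3 can remove allocated patients from ITT and safety, against the other definitions in both documents, and nothing says which governs. It should be settled before database lock.

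The likely numerical effect is small. Applied evenly, excluding 1% costs about 0.3 points of power (90.8% to 90.5%). If patients were removed from the Toujeo arm only, at 1% to 3% and with a 33% response, the shift would be 0.06 to 0.17 points, or about 1% to 3% of the planned 5.5-point difference. All these frequencies are assumptions.

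A reader might go further and conclude that the rule could produce about a fifth of the planned effect (1.19/5.5 = 0.22). That needs a 3% frequency, removal from one arm only, and no responder among those removed, all at once. Nothing in the documents supports that combination, so it is a bound and not an estimate. Nor do the documents show a deliberate departure from ITT.

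**What to change.** In SAP 2.3, limit the exclusion to patients with no IRT allocation at any time. Add that a patient prescribed or dispensed study drug before the call and later allocated stays in ITT in the allocated arm and, if treated, in the safety population.

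Add prescription or dispensing before the IRT call to the irregularities in SAP 2.2.1 and Table 3. Table 3 now names only dispensation without an IRT transaction, although its list is open. Identify cases by comparing dates, without regard to arm. If wanted, add a sensitivity analysis of the primary endpoint that excludes these patients.

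The cost is two sentences and one table row before lock. No new data are needed, and the planned sample size and alpha levels do not change.
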